1.2 Clinical perspective and study aim

In this prospective study we will perform multiparametric high resolution ultrasound in patients with known suspicious breast lesions (BI-RADS 4 and 5). We will acquire morphologic by conventional B-mode and 3D US and functional information about the lesions by examination of tumor vascularity and structure as expressed by means of stiffness. It can be expected that with this multiparametric US imaging an increased sensitivity and especially specificity of US of the breast can be achieved.

2. Patients and Methods

Over a period of 24 months 120 patients with breast lesions categorized as BI-RADS 4 and 5 (3) will be included in this prospective study- that means patients with suspicious lesions, planned to undergo an image-guided biopsy or surgery. This number of patients is necessary for a hypothesized improvement of the AUC by 10% (from 0.8 to 0.9) with a type I error of 5% and a type II error of 20%. The recruitment of patients will take place immediately after a breast clinical or imaging examination (mammography, ultrasound or MRI of the breast) demonstrating a suspicious breast lesion as described previously. All patients will be examined with multiparametric ultrasound. Contrast-enhanced examination will be conducted subsequently to the non contrast-enhanced one. The whole examination time will be approximately 30 minutes. Histopathology with either image-guided biopsy or surgery will be used as the standard of reference. Both in situ and invasive carcinomas will be regarded as a malignant (positive) result whereas benign and precursor lesions will be regarded as a benign (negative) result. In case of an image-guided biopsy, this will be performed immediately after the sonographic examination, whereas in the cases of planned surgery, this will be performed according to the planning of the respective Departments of Surgery or Gynecology.

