2.3.1.2 Image evaluation

Image evaluation of the B-mode ultrasound will be performed according to the revised ACR BI-RADS lexicon for ultrasound 5th edition, (3). Lesions will be evaluated for shape (oval, round or irregular), orientation (parallel or not), margin (circumscribed, microlobulated, indistinct, angular or spiculated), internal echogenicity (anechoic, hyperechoic, isoechoic, hypoechoic, heterogeneous or complex cystic and solid) and posterior acoustic features (none, enhancement, shadowing or combined pattern). Additionally on the coronal plane the presence or absence of retraction will be noted (22). The number and exact size of lesions in all 3 dimensions will be documented. Finally the likelihood of malignancy will be reported according to the ACR BI-RADS lexicon (3), with 4a = low suspicion for malignancy; 4b = moderate suspicion for malignancy; 4c = high suspicion for malignancy and 5 = highly suggestive of malignancy.

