2.5 Statistical evaluation

A McNemar test will be applied to the B-mode ultrasound alone and B-mode ultrasound with additional ultrasonographic examinations positive and negative results to determine statistical independence. ROC analysis will be performed to estimate the overall performance of B-mode ultrasound and multiparametric ultrasound. Using the histopathological data the numbers of true-negative (TN), true-positive (TP), false-negative (FN) and false-positive (FP) results for B-mode ultrasound and multiparametric US will be obtained and sensitivity, specificity, accuracy, positive predictive value (PPV) and negative predictive value (NVP) for both methods will be calculated.

3. Timetable

September 2015	Obtaining IRB approval
September 2015 to April 2017	Multiparametric ultrasound examinations according to protocol
May/June 2017	Statistical evaluation
July to September 2017	Preparation and submission of manuscripts

AMENDMENT TO THE STUDY PROTOCOL

Treatment of early breast cancer is usually surgical, comprising breast-conserving surgery for small, unifocal tumors, or mastectomy for larger or multicentric tumors. However, in women with locally aggressive disease or whose tumors display features that are predictive of early recurrence, neoadjuvant chemotherapy (NAC) is given to reduce the risk of recurrence. The early identification of chemotherapy responders and non-responders is crucial

in order to allow chemotherapy scheme modifications or changes to surgery or hormonal therapy, and thus provide optimal patient outcomes. Yet tumor response to NAC can be very different, resulting in fibrosis, concentric shrinking, fragmentation or change in the density of malignant tissue. All of these may affect the evaluation of residual tumor size (28).

Evaluation of tumor response to NAC is routinely done by using solely morphologic criteria (size reduction in mammography or B-mode ultrasound (US)), with US being more accurate than mammography in the evaluation of residual tumor size after NAC (28), showing a moderate correlation with the final histopathologic tumor size (29).

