However, the potentials of a multiparametric (mp) US have not yet been explored. We hypothesize that a functional imaging of the breast using high-resolution mp US allows an improved monitoring of therapy-induced changes before morphologic changes are visible (e.g. tumor-shrinkage). Our approach focuses on the assessment of specific imaging biomarkers, which help to differentiate treatment responders from non-responders immediately after onset of NAC. The aim of this study-phase is to acquire mp US data with CP/PD, elastography and CEUS for an improved assessment of early treatment response.

For this reason, 40 patients with breast cancer undergoing NAC will be imaged before, during and after NAC/pre-surgery with mp US imaging of the breast. This number of patients is necessary for a hypothesized improvement of the AUC by 20% (from 0.7 to 0.9) with a type I error of 5% and a type II error of 20%. The participants to this part of the study will be recruited among the patients, already taking part in the first part of the study and planned to receive a NAC, according to the recommendations of the interdisciplinary tumor board. Due to different underlying biochemical processes of the different US modalities, it can be assumed that the single modalities may have different time frames for the early detection of therapy-induced changes- yet literature data on this subject are sparse. To monitor therapy response, the patients will receive a baseline mp US examination (as already planned in the study protocol) and an additional mp US examinations on the 3rd day after the 1st cycle, in order to evaluate possible initial changes in tumor morphologic and functional parameters, induced by NAC, which might allow for an early

prediction of histologic response. Patients will be examined again in the week after the 2nd, 4th and 6th (last) cycles of NAC. In cases where 8 NAC cycles will be necessary, a further examination will be planned after the 8th cycle.

The image analysis will be conducted as described in the original study protocol.

Qualitative and quantitative imaging parameters will be correlated with histopathological tumor grade, microvascular density as an indicator of tumor-neoangiogenesis, hormone receptor status and other newer factors such as HER2-neu proliferative indices and gene expression profile before and after NAC.

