For the assessment of treatment response, functional imaging data of the baseline examination and of the examinations after the 1st, 2nd, 4th and 6th (+/- 8th) cycle will be compared for therapy-induced changes of both lesion morphology and functional capabilities by two experienced radiologists independently.

The statistical evaluation will be performed as described in the original study protocol.

CHANGES IN THE STUDY PROTOCOL

- Additional mp US examinations after the first, second, fourth and sixth (and after the eighth, if 8 NAC cycles are necessary) cycle of NAC.
- Correlation of qualitative and quantitative imaging parameters with histopathological tumor grade, microvascular density, hormone receptor status, HER2-neu, proliferative indices and gene expression profile before and after NAC.

4. Literature

2. Stavros AT. Breast ultrasound. Philadelphia: Lippincott, Williams and Wilkins; 2004.

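### The neoadjuvant phase is sized on an AUC gain from 0.7 to 0.9, but the analysis carried over to it has no test of that gain and no responder criterion

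*Combined protocol and SAP*

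**What the plan says.** The Amendment to the Study Protocol adds a phase of 40 breast cancer patients receiving neoadjuvant chemotherapy (NAC). The number is justified by a "hypothesized improvement of the AUC by 20% (from 0.7 to 0.9) with a type I error of 5" percent, and a type II error of 20%. The stated target is early "prediction of histologic response". The examinations are at baseline, on day 3 after cycle 1, and after cycles 2, 4 and 6 (and 8 where given).

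The analysis of this phase is one sentence: "The statistical evaluation will be performed as described in the original study protocol". Section 2.5 of that protocol contains:

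- one hypothesis test: "A McNemar test will be applied to the B-mode ultrasound alone and B-mode ultrasound with additional ultrasonographic examinations positive and negative results";
- ROC curves: "ROC analysis will be performed to estimate the overall performance of B-mode ultrasound and multiparametric ultrasound";
- the usual accuracy measures from true and false positives and negatives against histopathology.

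The class rule behind those counts is in section 2 (Patients and Methods): "Both in situ and invasive carcinomas will be regarded as a malignant (positive) result", with benign and precursor lesions as negative. Image analysis is also carried over unchanged.

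**The concern.** A type I and a type II error rate describe a particular test of a particular hypothesis. Here the hypothesis is a difference between two AUCs, and the carried-over analysis has no test of that difference. Its one test asks a different question: whether the two methods call positive equally often.

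The carried-over reference standard was written to separate cancer from non-cancer in part 1. In the amendment every patient has cancer and the contrast of interest is responder against non-responder, for which no criterion is given.

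The comparison that the phase is powered for can therefore be run only after someone supplies the response criterion, a rating for each method and a test. If that happens after outcome data have been seen, the stated 5% and 80% no longer describe the result. The criterion also sets the responder share, on which the power of 40 patients depends.

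**Working it through.** **Inputs.** From the amendment: N = 40, AUCs 0.7 and 0.9, type I error 5%, type II error 20%. Not in the documents, so assumed: responder share 20-50%, correlation r between the two AUCs, sidedness, cut-offs, no dropout.

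**1. The plan's own figure.** The number 40 can be neither confirmed nor refuted without the missing inputs. With n1 responders and n0 non-responders, the Hanley-McNeil variance is

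Var(A) = [A(1−A) + (n1−1)(Q1−A²) + (n0−1)(Q2−A²)] / (n1·n0), with Q1 = A/(2−A) and Q2 = 2A²/(1+A).

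For 20 and 20 patients:

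- A = 0.7: Q1 = 0.5385, Q2 = 0.5765, Var = 2.7737/400 = 0.006934.
- A = 0.9: Q1 = 0.8182, Q2 = 0.8526, Var = 1.0555/400 = 0.002639.
- With r = 0.5, the variance of the difference is 0.006934 + 0.002639 − 2(0.5)√(0.006934 × 0.002639) = 0.005295, so SE = 0.0728.
- Two-sided power = Φ(0.20/0.0728 − 1.960) = Φ(0.788) = 78.5%.
- N for 80% = 40 × 0.005295 × ((1.960 + 0.842)/0.20)² = 41.6, so 42.

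By the same method N is 39 at 40% responders with r = 0.6. Over the whole assumed range (r from 0 to 0.7) it runs from 29 (50% responders, r = 0.7) to 142 (20%, r = 0).

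**2. Power of a paired AUC test, if the plan had one.** Simulated DeLong test, 40 patients, equal-variance binormal scores, 20,000 runs per cell, r about 0.3 / 0.5 / 0.6:

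| Responders | Two-sided 5% | One-sided 5% |
|---|---|---|
| 8 of 40 | 50.9 / 61.2 / 70.5% | 64.9 / 75.4 / 83.4% |
| 20 of 40 | 69.1 / 82.2 / 90.0% | 80.5 / 90.4 / 95.2% |

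With 16 responders the two-sided figures are 67.3 / 80.3 / 88.5%.

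**3. What McNemar on calls measures.** It compares the two positive-call rates, each equal to p·sens + (1−p)(1−spec) for responder share p. Suppose each method is cut at its midpoint, so that sensitivity equals specificity: 64.5% at AUC 0.7 and 81.8% at AUC 0.9.

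- p = 0.5: 0.5(0.645) + 0.5(0.355) = 50%, and 0.5(0.818) + 0.5(0.182) = 50%. McNemar's null hypothesis is exactly true although the AUCs differ by 0.20.
- p = 0.2: 0.2(0.645) + 0.8(0.355) = 41.3%, and 0.2(0.818) + 0.8(0.182) = 30.9%.

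Simulated power of the exact test on calls, with the AUCs held at 0.7 and 0.9, N = 40 and score correlation 0.59 (r about 0.5):

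| Specificity, B-mode / multiparametric | 20% responders | 50% responders |
|---|---|---|
| midpoints (64.5 / 81.8%) | 14% | 2% |
| 40 / 80% | 94% | 57% |
| 50 / 90% | 97% | 69% |

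Other pairs give 4% (60 / 60%, 20% responders) and 97% (90 / 80%, 50% responders). A wider set of cut-offs spans about 1% to 98%. The AUC gain is the same in every cell; only the cut-offs and responder share change.

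**4. The class rule.** Section 2 separates carcinoma from benign or precursor lesions. Applied at diagnosis it puts all 40 patients in one class, so no ROC curve exists. The amendment names histologic response but gives no criterion that would divide them.

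**The case against.** *ROC analysis implies an AUC comparison.* Section 2.5 gives estimation as its purpose. Even if a comparison was intended, no test or interval is named, and the curves need a responder classification that is missing.

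*The comparator is already fixed.* This stands. Section 2.4 says multiparametric results are compared with B-mode results, and section 2.5 names B-mode alone against B-mode plus the additional examinations. What is missing is the B-mode response metric. A reader might infer that it must be size change, because the amendment notes "Evaluation of tumor response to NAC is routinely done by using solely morphologic criteria" and section 2.3.1.2 says "The number and exact size of lesions in all 3 dimensions will be documented". The documents do not support that narrowing: the same section records shape, margin, orientation, echogenicity and posterior features, and the amendment speaks of lesion morphology in general.

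*The early examination is evidently the main one.* This largely stands. The amendment ties early prediction to day 3 after cycle 1, and only the label of primary is missing. A reader might infer an inflated type I error from four or five follow-up examinations (1 − 0.95⁴ = 18.5%, 1 − 0.95⁵ = 22.6%, if independent). The plan does not say that each would be tested at 5%, so that is not claimed.

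*McNemar would usually miss the gain.* A reader who looks only at the midpoint rows might conclude this. It does not hold across cut-offs, and the documents give none. Nor does a high figure help: it reflects a shift in how often positives are called, which is not evidence of better separation of responders.

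**Conclusion.** The point holds as a mismatch between the sized hypothesis and the carried-over analysis. The 5% and 20% error rates belong to no test in the plan, the one test present does not track the AUC gain, and the one class rule present is not a responder criterion. These conclusions rest on the text alone. The missing rating and the missing primary label, taken by themselves, would only be gaps in detail.

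A reader might also infer that 40 patients are too few. The documents do not support that. A paired DeLong test has about 50-90% power two-sided and about 65-95% one-sided, and reaches about 80% two-sided at 40-50% responders with r about 0.5. Those ranges rest on assumed responder shares of 20-50%, r of about 0.3-0.6 and binormal scores, and the amendment does not state sidedness. The McNemar range rests in addition on assumed cut-offs.

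**What to change.** Replace the carry-over sentence in the amendment with an analysis of this phase, fixed before outcome data are seen, that:

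1. states the histologic-response criterion, chosen by the sponsor, as the reference standard in place of the rule in section 2;
2. makes one paired test of the two AUCs (for example DeLong, with a confidence interval for the difference) the primary analysis, for B-mode alone against B-mode plus the additional examinations, with McNemar and the accuracy measures secondary;
3. states how each method yields one ordered response rating. The sponsor chooses the B-mode metric, not necessarily size alone. Any multiparametric score is fixed in advance or, if fitted on the same 40 patients, corrected for optimism;
4. labels one examination as primary and the others as secondary. The early-response aim points to day 3 after cycle 1. However, the amendment itself expects functional change before visible shrinkage, so the sponsor should check that a B-mode AUC of 0.7 is plausible that early;
5. states the responder share, AUC correlation and sidedness behind 40, and restates the power if they do not give 80%.

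No new examinations are needed. The cost is amendment wording plus real work to define the rating. Findings at later examinations become secondary, and one primary examination may miss modalities that change at another time, which the amendment says is possible. The restated power may fall below 80%.
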